The elbow joint is made up of three bones: the humerus (upper arm bone), the radius and ulna (two bones in the forearm). At the distal end of the humerus there are two epicondyles, one lateral (on the outside) and one medial (on the inside). The area of maximal tenderness is usually an area just distal to the origin of the extensor muscles of the forearm at the lateral epicondyle. Most commonly, the extensor carpi radialis brevis (ECRB) is involved, but others may include the extensor digitorum, extensor carpi radialis longus (ECRL), and extensor carpi ulnaris. The radial nerve is also in close proximity to this region and divides into the superficial radial nerve and the posterior interosseous nerve.

Etiologies of Lateral epicondylitis

Lateral epicondylitis is classified as an overuse injury that may result in hyaline degeneration of the origin of the extensor tendon. Overuse of the muscles and tendons of the forearm and elbow together with repetitive contractions or manual tasks can put too much strain on the elbow tendons. These contractions or manual tasks require manipulation of the hand that causes maladaptation in tendon structure that lead to pain over the lateral epicondyle. Mostly, the pain is located anterior and distal from the lateral epicondyle.

Epicondylitis occurs at least five times more often and predominantly occurs on the lateral rather than on the medial aspect of the joint, with a 4:1 to 7:1 ratio. It affects 1-3% of the population, with those 35-50 years old most commonly being affected. If a patient is <35, it is important to consider differential diagnosis (growth plate disorder, referral from the cervical spine. If a patient is >50, consider OA, referred cervical spine pain.

This injury is often work-related, any activity involving wrist extension, pronation or supination during manual labor, housework and hobbies are considered as important causal factors. Lateral epicondylitis is equally common in both sexes. Between the ages of 30-50 years the disease is most prevalent. Obtaining of the condition at the both lateral epicondyle is rare, the dominant arm has the greatest chance of the occurrence of lateral epicondylitis. Twenty percent of cases persist for more than a year.

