A systematic review identified 3 risk factors: handling tools heavier than 1 kg, handling loads heavier than 20 kg at least 10 times per day, and repetitive movements for more than 2 hours per day. Other risk factors are overuse, repetitive movements, training errors, misalignments, flexibility problems, aging, poor circulation, strength deficits or muscle imbalance and psychological factors^{lxxxix}.

There are several opinions concerning the cause of lateral epicondylitis:

1. Inflammation
 - a. Although the term epicondylitis implies the presence of an inflammatory condition, inflammation is present only in the earliest stages of the disease process^{xc}.
2. Microscopic tearing
 - a. Nirschl and Pettrone attributed the cause to microscopic tearing with formation of reparative tissue (angiofibroblastic hyperplasia) in the origin of the extensor carpi radialis brevis (ECRB) muscle. This micro-tearing and repair response can lead to macroscopic tearing and structural failure of the origin of the ECRB muscle.
 - b. Histology of tissue samples shows "collagen disorientation, disorganization, and fibre separation by increased proteoglycan content, increased cellularity, neovascularization, with local necrosis." Nirschl termed these histological findings bangiofibroblastic hyperplasia. The term has since been modified to bangiofibroblastic tendinosis. He noted that the tissue was characterized by disorganized, immature collagen formation with immature fibroblastic and vascular elements. This grey, friable tissue is found in association with varying degrees of tearing involving the extensor carpi radialis brevis.
3. Degenerative Process
 - a. The histopathological features of 11 patients who had lateral epicondylitis were examined by Regan et al. They determined that the cause of lateral epicondylitis was more indicative of a degenerative process than an inflammatory process. The condition is degenerative with increased fibroblasts, vascular hyperplasia, proteoglycans and glycosaminoglycans, and disorganized and immature collagen.
 - b. Repetitive eccentric or concentric overloading of the extensor muscle mass is thought to be the cause of this angiofibroblastic tendinosis of the ECRB. Epicondylitis is a degenerative condition in which increased fibroblastic activity and granulation tissue formation occur within the tendon^{xcii}.
4. Hypovascularity

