 - a. Because this tendinous region contains areas that are relatively hypovascular, the tendinous unit is unable to respond adequately to repetitive forces transmitted through the muscle, resulting in declining functional tolerance^{xcii}.

Symptoms

The most prominent symptom of epicondylitis lateralis is pain, this pain can be produced by palpation on the extensor muscles origin on the lateral epicondyle. The pain can radiate upwards along the upper arm and downwards along the outside of the forearm and in rare cases even to the third and fourth fingers. It is also often seen that the flexibility and strength in the wrist extensor and posterior shoulder muscles are deficient^{xciii}. Furthermore, it is also often seen that the flexibility and strength in the wrist extensor and posterior shoulder muscles are deficient. At least patients report weakness in their grip strength or difficulty carrying objects in their hand, especially with the elbow extended. This weakness is due to finger extensor and supinator weakness^{xciv}.

Symptoms last, on average, from 2 weeks to 2 years. 89% of the patients recover within 1 year without any treatment except perhaps avoidance of the painful movements^{xcv}.

MR5® Prototype Device for temporary adjunctive use to relieve pain associated with Lateral Epicondylitis.

Subjective Assessment

- Onset of pain 24-72 hours after provocative activity involving wrist extension
- Pain may radiate down forearm as far as the wrist and hand
- Difficulty with lift and grip (Pain+/- weakness)

Objective Assessment^{xcvi}

- Pain and point tenderness over lateral epicondyle and/or 1-2cm distal to epicondyle
- Pain and weakness on resisted wrist extension
- Weakness on grip strength testing (Dynamometer)
- Pain and/or decreased movement on passive elbow extension, wrist flexion and ulnar deviation and pronation
- Weak elbow extensors and flexors

Differential Diagnosis

- Radial Tunnel Syndrome
- Pain in the posterolateral area of the forearm
- Pain sometimes spreads to the dorsal side of the wrist
- Paresthesia
- Weakness (overuse injuries of the musculoskeletal system)
- Posterior Interosseous Syndrome
- Motor deficits
- Elbow osteoarthritis
- Fractures
- Distal Radial Fractures
- Radial Head Fracture
- Olecranon Fracture
- Cervical Radiculopathy
- Radiating arm pain corresponding to the dermatomes
- Neck pain
- Paresthesia
- Muscle weakness in myotome
- Reflex impairment/loss
- Headaches
- Scapular pain

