The informed consent form that will be used in this clinical study is contained in **Appendix D**.

ASSIGNMENT OF SUBJECT IDENTIFICATION NUMBER

The subject will be assigned a unique subject identification number based upon his or her order of entry into the study.

Additional information about the informed consent and subject ID number assignment is contained in a later section of the protocol titled, "SAFETY AND CONFIDENTIALITY ISSUES."

STUDY QUALIFICATION EVALUATION: INCLUSIONS/EXCLUSION CRITERION

INCLUSION CRITERIA

To be eligible for study participation, a subject must satisfy each of the following criteria.

Patient history: History of one or more the following:

- Patients with a history of pain around the Lateral Epicondyle for at least 1 month;
- Tenderness localized to the epicondyle and anterodistal region of the epicondyle with palpation;

- 2 of 4 positive results of provocative tests comprising of Maudsley's, Cozen's, Thomsen and Mill's tests (Whaley, Baker 2004);
- Aged between 18 and 50 years;
- Both genders.

Reference - Whaley AL, Baker CL. *Lateral epicondylitis. Clin Sports Med.* 2004; 23(4):677-691

Medication Use History: Where applicable, history of attaining relief from Lateral Epicondyle pain from taking over-the-counter and/or prescription muscle relaxants; nonsteroidal anti-inflammatories (NSAIDs) such as ibuprofen or naproxen, and acetaminophen.

Previous Records Review (x-rays, MRI, CT scans, etc.): where pre-existing and available, previous records review that indicates muscle or ligament injury and the absence of Degenerative Joint Disorder (DJD)

Physical Examination of the Lateral Epicondyle Region.

- Painful range of motion
- Pain and weakness upon grip strength and wrist extension
- Muscles in Lateral Epicondyle feel hard, tight or knotted upon palpation
- Muscles in Lateral Epicondyle feel hard, tight or knotted upon palpation
- Lateral Epicondyle pain is persisting over one month
- Self-reported Degree of Pain rating on the 0-100 VAS pain scale for the Lateral Epicondyle region is 50 or greater

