- Subject is willing and able to maintain his or her current pre-study Lateral Epicondyle pain management regimen of pain relief medication and/or treatment/therapy use throughout the course of study duration, whilst refraining from consuming other OTC and/or prescription medication(s) and/or herbal supplements intended for the relief of pain and/or inflammation, including muscle relaxants, and/or partaking in other treatments/therapies including conventional therapies such as physical therapy, occupational therapy and hot or cold packs, as well as alternative therapies such as chiropractic care and acupuncture.
- 18 years of age or older
- Male or female
- Subject is fluent in Portuguese

EXCLUSION CRITERIA

A subject who satisfies any of the following criteria will be excluded from study participation:

- hemophilia or any type of blood clotting disorder
- chronic immune impairment neoplasia
- neurologic deficits
- cervical radiculopathy
- peripheral nerve disease
- rheumatoid arthritis
- shoulder disease
- radial tunnel syndrome
- previous surgery of the affected upper extremities
- congenital or acquired bony deformity in the ipsilateral upper extremity
- the initiation of opioid analgesia or corticosteroid or analgesic injection interventions within the previous 6 months

- physical therapy intervention on the upper extremity in the previous year
- bilateral epicondylitis
- secondary orthopedic problems.

Physical Examination of the Lateral Epicondyle Region:

- Lateral Epicondyle pain is acute, defined as having persisted over less than the last 1 month
- Self-reported Degree of Pain rating on the 0-100 VAS pain scale for the Lateral Epicondyle region is less than 50
- Local corticosteroids and/or botulinum toxin (Botox®) injection for Lateral Epicondyle pain relief within the prior 30 days
- Medical tx; such as chiropractic care and acupuncture within last 30 days
- Current, active chronic pain disease: chronic fatigue syndrome, fibromyalgia, endometriosis, inflammatory bowel disease, interstitial cystitis diabetic neuropathic pain
- Cancer or treatment for cancer in the past 6 months, including tumors of the spinal cord
- Diabetes Type 1
- Significant heart conditions including CHF and implantable heart devices such as a pacemaker
- Active infection, wound, or other external trauma to the areas to be treated with the laser
- Medical, physical, or other contraindications for, or sensitivity to, light therapy

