2) **Parametric ANCOVA model** analysis with the mean change from baseline to study endpoint in Lateral Epicondyle pain ratings on the VAS as the dependent variable, procedure group as the independent variable of interest and baseline average Lateral Epicondyle pain VAS rating as a covariate. A two-tailed significance level of 5% will be considered to be statistically significant.

Covariates: The following potential covariate baseline variables will be adjusted, as applicable, through application of an ANCOVA analysis for the continuous variables and linear regression analysis for categorical variables.

- Baseline Lateral Epicondyle pain VAS rating
- Fitzpatrick Skin Type Classification
- Age
- Gender
- Demographics

SUPPORTIVE OUTCOME MEASURES

The following supportive outcome measures will be evaluated:

- a. Mean and individual subject changes in Degree of Pain VAS ratings across and between all study evaluation time points, within and between procedure groups
- b. Mean and individual subject changes in each of the PRTEE, grip strength and TNFa levels measurements across and between all evaluation points, within and between procedure groups
- c. Differences in satisfaction with Study Outcome Ratings between procedure groups at both evaluated time points, and any change between

SUPPORTIVE MEASURES STATISTICAL EVALUATION METHODS

- a. Supportive measures that are continuous variables will be analyzed through parametric analysis using ANCOVA. A two-way significance level of 5% will be statistically significant.
- b. Supportive measures that are categorical will be evaluated through linear regression analysis.
- c. Satisfaction with Study Outcome Ratings: will be tabulated according to category and reported as percentages. Satisfaction levels will be correlated with subject individual study success and recorded changes in Lateral Epicondyle pain VAS ratings from baseline to endpoint evaluations.

STATISTICAL EVALUATION OF APPLICATION OF PAIN MANAGEMENT REGIMEN

The impact of pain management regimen use on the study outcome measure will be evaluated through application of the following analyses:

- a. **Fisher's exact test** to compare the proportion of subjects requiring use of his or her individualized pain management regimen between the test and the control groups.

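### Pain duration has a one-month floor and no ceiling at entry, but it is not a covariate, a stratum or a planned balance check

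*Combined protocol and SAP*

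**What the plan says.** **Entry.** INCLUSION CRITERIA sets a minimum duration twice: "Patients with a history of pain around the Lateral Epicondyle for at least 1 month" and, under the physical examination, "Lateral Epicondyle pain is persisting over one month". EXCLUSION CRITERIA repeats the same floor from the other side: "Lateral Epicondyle pain is acute, defined as having persisted over less than the last 1 month". No maximum appears anywhere.

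**Natural course.** Under Symptoms: "Symptoms last, on average, from 2 weeks to 2 years", and "89% of the patients recover within 1 year without any treatment except perhaps avoidance of the painful movements". Under Etiologies of Lateral epicondylitis: "Twenty percent of cases persist for more than a year". The two one-year figures differ (89% resolved against an implied 80%), but both say that most cases resolve.

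**Analysis.** PRIMARY EFFICACY OUTCOME STATISTICAL EVALUATION METHODS names two primary analyses.
- Fisher's exact test on responders is unadjusted. It rests on the premise that randomization was done properly and that the covariates that matter came out alike in the two arms.
- The ANCOVA of VAS change has baseline average VAS as its only covariate.

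The Covariates paragraph then says that "The following potential covariate baseline variables will be adjusted, as applicable, through application of an ANCOVA analysis for the continuous variables", with a regression for categorical ones, and lists baseline VAS, Fitzpatrick skin type, age, gender and demographics. RANDOMIZATION stratifies by skin type grouping; the sample stratification plan sets this out by site. PRE-PROCEDURE VARIABLES includes an item for baseline lateral epicondyle pain variables. Its content is not defined, and no analysis uses it.

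**The concern.** On the protocol's own account, a subject five weeks into an episode and one eighteen months into it are both eligible and may be at different points of a mostly self-limiting course. If duration predicts the three-week change in pain, leaving it out of the ANCOVA leaves explainable variance in the error term. With 25-30 subjects per arm, short- and long-standing cases could also split unevenly by chance without anyone seeing it, because the analysis section does not commit to showing duration by arm. That matters for this plan in particular, since the unadjusted responder test is defended by the claim that important covariates are balanced. Any adjustment also has to be named in advance: one chosen after an imbalance has been seen is post hoc.

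**Working it through.** The plan gives no figure for duration, so there is nothing of its own to reproduce. The documents supply neither the mix of durations nor the link between duration and three-week response. Every size below therefore rests on a stated assumption.

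**Inputs from the protocol.** 30 enrolled and 25 available per arm; anticipated response 50% and 20% (Rationale for sample size). Primary time point within 24 hours after the three-week procedure phase (Evaluation Time Points). These are taken as stated; the point does not depend on whether the sample size is right.

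**1. Is duration used anywhere?**

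| Place | Variables named | Duration? |
|---|---|---|
| Randomization strata | skin type grouping (planned by site) | no |
| Primary Fisher's test | none | no |
| Primary ANCOVA | baseline average VAS | no |
| Covariate list | VAS, skin type, age, gender, demographics | no |
| Baseline pain variables | not defined | cannot be told |

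Symptom duration is a disease characteristic, so the word demographics does not cover it. The qualifier that adjustment is made where applicable does not add a variable that is not listed.

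**2. Precision in the ANCOVA.** Let R² be the share of residual VAS-change variance that duration explains (assumed). The standard error is multiplied by √(1 − R²):
- R² = 0: √1 = 1, no gain
- R² = 0.05: √0.95 = 0.975, about 2.5% shorter
- R² = 0.20: √0.80 = 0.894, about 10.6% shorter

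Put as power, a correlation of 0.2-0.4 between duration and outcome (R² = 0.04-0.16) lifts a nominal 80% to about 82-86% at 30 per arm.

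**3. Chance imbalance.** Treat duration as short or long, with 30-50% short (assumed). The exact binomial probability that the arms differ by 20 points or more, in either direction, is:

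| | 30% short | 50% short |
|---|---|---|
| 30 per arm | 0.120 | 0.155 |
| 25 per arm | 0.164 | 0.203 |

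Check of the 0.155: 2 × P(Bin(60, 0.5) ≥ 36) = 0.155.

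**4. Effect of such an imbalance.** Shift in the responder difference = imbalance × gap in response rate between short and long cases. With an assumed gap of 20-40 points, a 20-point imbalance gives 0.20 × 0.20 = 4 points to 0.20 × 0.40 = 8 points. With no gap the shift is zero.

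**5. Type I error.** In 20,000 simulated trials per setting (30 per arm, half short, 20% response in both arms), Fisher's test rejected in about 2% of trials, whether the gap was 0, 20, 30 or 40 points. Leaving duration out does not raise the false-positive rate.

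**6. Responder endpoint.** In the same simulation with 50% against 20%, power was about 0.59-0.61 for Fisher's test at every gap. For a duration-stratified Cochran-Mantel-Haenszel test it was 0.69 with no gap and 0.71-0.79 with a gap of 20-40 points. Only the part above 0.69, about 2-10 percentage points, comes from duration. The rest is Fisher's conservatism.

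**The case against.** The case for leaving the plan alone is substantial, and most of it stands.

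- **Randomization already deals with this in expectation.** Chance imbalance is part of the ordinary standard error. At 30 per arm with half short, the SD of the imbalance is √(2 × 0.25/30) = 0.129. A gap of 20-40 points turns that into a typical shift of 2.6-5.2 points, against a standard error of √((0.25 + 0.16)/30) = 0.117, or 11.7 points. This stands: there is no systematic bias.
- **The prognostic link is not shown.** A reader might spread the one-year recovery figures evenly over time and conclude that spontaneous recovery supplies much of the assumed 20% placebo response. The documents do not support that. A constant recovery rate would give a five-week and an eighteen-month case the same outlook, so duration would be uninformative. The figures describe full recovery in patients at large, whereas a responder needs only a 30% fall in VAS. Trial subjects must also still rate 50 or more at screening and on the three-day average after stabilization.
- **A different mechanism in early disease is conjecture.** The protocol says "inflammation is present only in the earliest stages of the disease process" and credits the device partly with anti-inflammatory action, so a reader might infer that early and late cases respond differently. That statement sits in a list of competing opinions on cause, and the background calls the pathophysiology unclear. A main-effect covariate would not test it anyway.
- **Duration may already be recorded, or may not.** Eligibility needs only a yes or no at one month. The undefined pain variables could include it, and the case report forms are not in the available text. Neither collection nor its absence can be asserted.
- **Fisher's test takes no covariates,** so a longer covariate list does not reach the primary responder test. This stands, and it limits the fix to the ANCOVA.
- **Open entry fits the proposed indication,** which has no duration limit. No change to eligibility follows from this point.

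What survives is narrower. The plan relies on balance in important covariates, the protocol describes a course that varies widely in length, and duration is neither adjusted for nor set to be displayed.

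**Conclusion.** The omission is real and its consequence modest. It is a matter of precision and transparency at 25-30 per arm, not of validity. A reader might infer that early recoverers could manufacture a device effect; randomization and the unchanged type I error rule that out as a systematic problem. The benefit of adjustment cannot be sized from the documents. On the assumption that duration explains 5-20% of residual VAS-change variance, the standard error shortens by about 2.5-11%; if it explains none, there is no gain. The case for acting is that the change is cheap and must be made before unblinding to count.

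**What to change.** 1. Under PRE-PROCEDURE VARIABLES, state that the baseline pain variables include duration of the current lateral epicondyle pain in months, recorded as a number.
2. In the analysis section, add log duration as a prespecified continuous covariate in the VAS-change ANCOVA and to the covariate list. The log suits a variable with a floor of one month and no ceiling.
3. Tabulate duration by arm, so that the balance premise behind the unadjusted test can be inspected.
4. Keep Fisher's exact test as the primary responder test. A duration-adjusted responder analysis is optional; if included, it should be fully specified in advance and labelled supportive only.

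Eligibility and treatment are untouched. The cost is one recorded field (none if the case report form already has it), one degree of freedom and one table row, plus one supportive model if the optional analysis is adopted.

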- Overall study success criteria of at least a 30% difference between the test device group and the placebo group, comparing the proportion of individual successes in each group.
- It is anticipated that about 50% of subjects in the test device group and about 20% of subjects in the placebo group will meet the individual success criteria, and
- Intended application of a two-tailed test with an alpha value of 0.05 and Power of 0.8

- the sample size of 25 available subjects per group (test group and the control group, separately) has been determined using the following reference calculator: *Hypothesis Testing: Categorical Data - Estimation of Sample Size and Power for Comparing Two Binomial Proportions* in Bernard Rosner's *Fundamentals of Biostatistics*.

For the purposes of sample size calculation, a subject loss-to-follow-up of 20% is anticipated.

Therefore, a minimum starting sample size of 30 evaluable subjects in each group is needed to ensure that a sufficient number remains at the end of the trial (25 subjects per group) for any significant differences found between groups to be considered statistically valid and representative of the general population being sampled. This results in a total of 60 subjects being enrolled in this study across both study procedure groups.

RANDOMIZATION

Subject allocation to procedure group will be via variable block randomization with varying block sizes of two and four used at random to minimize the likelihood of predicting the next procedure group assignment. In addition, randomization will be stratified by Fitzpatrick Skin Type grouping

Randomization will be attained using computer generation sequence methodology, ensuring that the randomization methodology and the generated allocation sequence is concealed from the investigator and subjects.

Concealment will be insured as follows:

- Each computer-generated randomization sequence is unique and will therefore not be able to be replicated.
- Randomization will occur to either 'Test Group A' or 'B' rather than to a tests or placebo group, and only the study Sponsor will know which assignment corresponds to the active devices and which corresponds to the fake device. The Sponsor will not reveal this information to any source (investigators, subjects, or study Monitor) until the final study data analysis is complete.

TRIPLE BLIND DESIGN

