The pre-procedure assessment phase will commence following successful completion of the individualized pain management regimen stabilization phase and just prior to commencement of the procedure administration phase.

CONTINUED STUDY ELIGIBILITY EVALUATION

Prior to the subject commencing the Pre-Procedure Assessment phase of the study, the investigator will:

- review the subject's recordings of use/application of his or her individualized pain management regimen to ensure it was correctly applied and recorded, and that there are no deviations significant enough to warrant withdrawal of the subject from the study prior to entry to the pre-procedure assessment phase; and
- calculate the average of the 3 VAS degree of pain scores recorded during the last three days of the individualized pain management regimen stabilization phase. In order for the subject to proceed, the 3-day average VAS score must be 50 or greater. If it is less than 50, the subject's participation in the study ends at this time.

PRE-PROCEDURE MEASURES

- Degree of Pain Rating. This will occur within 15 minutes prior to the initial procedure administration. The exact time the VAS rating is recorded will be noted.
- PRTEE, Grip Strength and TNFa measurements will be noted.

PRE-PROCEDURE VARIABLES

- Baseline concomitant medication and treatment/therapy use
- Historical pain medication and treatment/therapy use
- Baseline Lateral Epicondyle pain variables
- PRTEE, Grip Strength and TNFa measurements and Fitzpatrick Skin Type Classification will be noted.
- Demographics

PROCEDURE ADMINISTRATION PHASE

PROCEDURE ADMINISTRATION PROTOCOL

- The procedure administration phase of the study will commence within 15 minutes subsequent to completion of the pre-procedure assessment phase.
- The procedure administration phase comprises a total of six procedure administrations with the Multi Radiance Medical® MR5® Prototype Device: two

procedures a week for three consecutive weeks*, each procedure administration three to four days apart.

[figure not shown]
- *Three weeks, 2 times a week... Follow-up at 4th week after administration phase*

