- b. **Parametric ANCOVA model** analysis with the mean change from baseline to study endpoint in Lateral Epicondyle pain ratings on the VAS as the dependent variable, procedure group as the independent variable of interest and average dosage/frequency of use any component of the individualized pain management regimen. A two-tailed significance level of 5% will be considered to be statistically significant.
- c. **T-test analysis** to compare the frequency of usage of the pain management regimen across study duration between treatment groups.

- d. **Linear regression analysis** to evaluate the impact of frequency of usage of the pain management regimen across study duration on the primary outcome measure between procedure groups
- e. **Log Rank statistics** to evaluate differences in the time to first use of the pain management regimen between test and placebo procedure groups

BLINDING EFFICACY EVALUATION

Statistical evaluation of blinding efficacy will be performed as follows:

- (i) The percentage of subjects who correctly perceived their procedure group assignment and the percentage of subjects who did not correctly perceive their procedure group assignment will be calculated.
- (ii) The percentage of times the administration investigators correctly perceived subjects' procedure group assignment and the percentage of times the assessment investigators did not correctly perceive subjects' procedure group assignment will be calculated.
- (iii) The percentage of times the assessment investigators correctly perceived subjects' procedure group assignment and the percentage of times the assessment investigators did not correctly perceive subjects' procedure group assignment will be calculated.
- (iv) The **Fischer's Exact categorical analysis technique** for comparison of proportion of successes (accurate procedure group assignment determination) and failures (inaccurate procedure group assignment determination) between subject groups will be performed for each of the subject, administration investigator and assessment investigator determinations.
 - Comparisons will be made to evaluate if the proportion of correctly guessed subject procedure group assignments is greater than the proportion of incorrectly guessed subject group assignments.
 - Comparison will be made for each of the groups of subjects, administration investigators and assessment investigators, within and between treatment groups.

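### The ANCOVAs of change in PRTEE, grip strength and TNF-alpha name no covariate, and the pain-regimen ANCOVA of VAS change is written without baseline VAS; run on the listed terms, these supportive analyses lose precision

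*Combined protocol and SAP*

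**What the plan says.** Under PRE-PROCEDURE MEASURES the protocol collects the baselines at issue: "PRTEE, Grip Strength and TNFa measurements will be noted". SUPPORTIVE OUTCOME MEASURES, item b, then defines the outcomes as changes: "Mean and individual subject changes in each of the PRTEE, grip strength and TNFa levels measurements across and between all evaluation points". The method, in SUPPORTIVE MEASURES STATISTICAL EVALUATION METHODS, item a, is one line: "Supportive measures that are continuous variables will be analyzed through parametric analysis using ANCOVA". A significance level follows, but no model terms.

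The only covariate list stands under PRIMARY EFFICACY OUTCOME STATISTICAL EVALUATION METHODS and opens: "The following potential covariate baseline variables will be adjusted, as applicable, through application of an ANCOVA analysis for the continuous variables". Its first entry is "Baseline Lateral Epicondyle pain VAS rating"; the others are Fitzpatrick skin type, age, gender and demographics. No baseline PRTEE, grip strength or TNF-alpha appears there or in any model.

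Two ANCOVAs in the plan have change in VAS as the dependent variable. The primary one (item 2 of the primary methods) has "baseline average Lateral Epicondyle pain VAS rating as a covariate". The other, STATISTICAL EVALUATION OF APPLICATION OF PAIN MANAGEMENT REGIMEN, item b, gives its terms as "procedure group as the independent variable of interest and average dosage/frequency of use any component of the individualized pain management regimen" and does not mention baseline VAS.

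**The concern.** When an outcome is analysed as a change from baseline, its own baseline is usually the most useful covariate. Without it, the error variance is larger, and any chance difference between arms at baseline passes into the comparison through regression to the mean. With 25 to 30 subjects per arm such chance differences are to be expected.

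An analyst who follows the text literally has two options for grip strength: no covariate, or the general list, which adjusts for baseline pain but not baseline grip. For the regimen analysis, the literal model leaves out a term that the plan itself uses for the same dependent variable. At stake is precision in supportive results that are meant to back a regulatory submission, together with a covariate choice left open until the data are in hand.

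**Working it through.** The plan states no sample size, SD or power for any supportive ANCOVA, so there is no figure of its own to reproduce here. Its figure of 25 completers per arm (30 enrolled) was derived for the primary responder comparison. I take 25 and 30 only as the numbers likely to be analysed. The test level is two-sided 0.05, as in the sample size rationale ("Intended application of a two-tailed test with an alpha value of 0.05 and Power of 0.8").

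**Assumptions.** SD is the same at baseline and follow-up, and the baseline-to-follow-up correlation is rho. The documents give neither, so rho is shown as a range. Equal SDs are a less safe assumption for VAS, because entry requires a rating of 50 or more.

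**Step 1: variance per subject.**
- Unadjusted change: 2(1 − rho)SD².
- ANCOVA with own baseline: (1 − rho²)SD² = (1 − rho)(1 + rho)SD².
- Ratio: 2/(1 + rho).

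| rho | Variance ratio | SE ratio (square root) | 25 per arm on change is worth, with own baseline |
|---|---|---|---|
| 0.3 | 2/1.3 = 1.54 | 1.24 | 25 × 1.3/2, about 16 |
| 0.5 | 2/1.5 = 1.33 | 1.15 | 25 × 1.5/2, about 19 |
| 0.7 | 2/1.7 = 1.18 | 1.08 | 25 × 1.7/2, about 21 |
| 0.9 | 2/1.9 = 1.05 | 1.03 | 25 × 1.9/2, about 24 |

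**Step 2: baseline VAS used in place of own baseline.** Let c be the correlation of baseline VAS with the outcome's own baseline, and suppose VAS relates to follow-up only through that baseline. The variance of change is then 2(1 − rho) − c²(1 − rho)² in SD² units, and the ratio to own-baseline ANCOVA is [2 − c²(1 − rho)]/(1 + rho). For c from 0.5 down to 0.3 the ratio is 1.40 to 1.49 at rho 0.3, 1.25 to 1.30 at rho 0.5, and 1.13 to 1.16 at rho 0.7. Most of the loss remains.

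**Step 3: what this means for PRTEE.** The protocol quotes 11 points as a substantial mean reduction in a group. I borrow it as a difference between arms, which is an assumption, with an assumed SD of 18. Two-sample t power, unadjusted change against own-baseline ANCOVA:

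| rho | 25 per arm | 30 per arm |
|---|---|---|
| 0.3 | 43% v 60% | 50% v 68% |
| 0.5 | 56% v 69% | 64% v 77% |
| 0.7 | 78% v 84% | 85% v 90% |

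At 30 per arm and rho 0.5, SD 15 gives 80% v 90% and SD 20 gives 55% v 68%. With c = 0.5 and baseline VAS adjusted for, SD 18 gives 67% v 77%. The gain fades as rho rises: at SD 15 and rho 0.7 it is 95.0% v 97.4%, and at rho 0.8 it is 0.3, 1.5 and 2.5 points for SD 15, 18 and 20. Nothing comparable was computed for grip strength or TNF-alpha.

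**Step 4: chance imbalance.** With equal SDs the slope of change on baseline is −(1 − rho). At rho 0.5, each point of chance difference between arms at baseline moves the unadjusted difference in change by half a point.

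**The case against.** A reader might infer that the plan excludes own-baseline adjustment for PRTEE, grip strength and TNF-alpha. The text does not support that. Item a of the supportive methods is silent; ANCOVA implies some covariate, and the fully specified primary ANCOVA uses the outcome's own baseline. The gap is one of specification. Nor is VAS the only baseline covariate listed: skin type, age, gender and demographics are there too. VAS is the only outcome baseline.

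The reach of the covariate list also matters. If it governs every ANCOVA in the plan, its discretionary wording could bring baseline VAS into the regimen model, and that half of the point falls away. If it is confined to the primary methods, where it stands, nothing says that grip strength would be adjusted for pain. This stands as a limit: the worst reading of both halves cannot be held at once. On either reading, though, no sentence names the own baseline of the three supportive outcomes.

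The regimen sentence is loosely built and gives regimen use no explicit role, so it may not be an exhaustive model. It still shows that in this plan the word ANCOVA does not reliably signal own-baseline adjustment.

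Finally, leaving out a baseline under randomisation costs precision and does not bias the estimator on average. A reader might also infer that the efficacy conclusion is at risk. It is not: the primary Fisher test does not involve these models, and the primary VAS ANCOVA has its baseline.

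**Conclusion.** The point holds as a gap in specification with a cost in precision. If the supportive ANCOVAs are run on the terms the plan lists, they are less precise than own-baseline ANCOVA. Against an unadjusted change score the variance penalty is 54%, 33% and 18% at rho 0.3, 0.5 and 0.7, and 5% at 0.9. It is somewhat smaller if baseline VAS is adjusted for. In the PRTEE illustration at 30 per arm, the power gain is about 10 to 12 points at rho 0.5 across SD 15 to 20, and under 3 points at rho 0.8.

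The direction holds for any rho below 1 under equal SDs. The size rests on assumed values of rho and SD, and on an 11-point figure that the protocol gives for change within a group. The consequence is confined to supportive analyses.

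**What to change.** In SUPPORTIVE MEASURES STATISTICAL EVALUATION METHODS, item a, state that each continuous supportive outcome is modelled by ANCOVA with procedure group, the pre-procedure value of that same outcome, and the skin-type randomisation stratum (I–III or IV–VI). In STATISTICAL EVALUATION OF APPLICATION OF PAIN MANAGEMENT REGIMEN, item b, add the same baseline VAS that the primary ANCOVA uses.

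All these values are already collected, so the change is to wording only. In the supportive models it costs one degree of freedom for own baseline and one for the two-level stratum; with 50 completers, 50 − 4 = 46 residual degrees of freedom remain. The regimen model loses one.

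Adding baseline VAS does not settle a separate matter in the regimen model: regimen use is measured after randomisation, so adjusting for it raises a question of bias that baseline adjustment cannot remove.
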